### 8.1.15 Pharmacodynamic Sample Collection

MMN will be used as a PD assessment. At each testing session, the following PD assessments will be performed during the EEG: MMN, P50, gamma power, and P300. Collection of P50 may be omitted if the essential equipment is not available. The testing session during each Treatment Period will begin approximately 1.5 hours after administration of study drug.

### 8.1.16 Pharmacodynamic Parameters

All EEG parameters will be obtained in accordance with the EEG acquisition guideline provided by Cerevance or their designee. It is anticipated that each EEG procedure will take approximately 4 hours to complete, including approximately 30 minutes to set up, 3 hours acquisition time, and 30 minutes to clean up.

#### MMN

MMN is a pre-attentive auditory component elicited by deviant stimuli in an auditory oddball task. MMN predominantly reflects activation of neuronal ensembles within primary auditory cortex, and thus indexes sensory level disturbance in schizophrenia. MMN will be obtained independently to pitch and duration deviant stimuli. MMN is maximal at frontocentral electrodes (Fz, Cz). Mean peak amplitude at 5 electrodes surrounding Fz within a predefined latency range will be the primary outcome measure.

## **P50**

P50 auditory evoked potentials will be recorded. Participants will be seated and instructed to relax and to focus their eyes on a fixation point. Stimulus signal of 90-dB pulses of 0.1 msec in duration will be generated and recorded the event-related potential waveforms.

32 pairs of auditory clicks will be presented every 10 seconds, with a 500 msec interclick interval.

The conditioning P50 wave (S1) and test P50 wave (S2) will be identified as the power in the alpha/beta frequency bands as suggested by Smucny et al. ([Smucny, 2013](#)). The data from the vertex (Cz) and surrounding electrodes will be collected and the P50 gating ratios will be calculated as the ratio of the test P50 to the conditioning P50 power. In case the Cz gating ratio is >0.2 units above the surrounding electrodes, the value will be discarded and replaced with the value from surrounding electrodes. P50 ratio will be defined as the ratio of S2/S1 power. The S2-S1 difference score as suggested by Smucny et al. ([Smucny, 2013](#)) will be used as an exploratory outcome measure.

## **Quantitative Electroencephalogram, Gamma Power**

Five minute eyes open/close recordings will be obtained during each recording session. Ten 1-second, artifact-free epochs will be chosen for quantitative analysis. Primary outcome measures will consist of power within delta (0.5 – 4 Hz), theta (4-7 Hz), alpha (8-13 Hz), delta (13-20 Hz), low gamma (20-40 Hz) and high gamma (40 – 60 Hz) over predesignated frontal, central, temporal and occipital sites. In addition, specific measures of 40 Hz activity will be assessed in response to repetitive 40 Hz auditory stimulation.

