#### 4.2.3 Exploratory Endpoints

- Mean P50 ratio (S2/S1) at 5 electrodes surrounding Cz following administration of CVN058 compared to placebo
- Mean P50 differences (S2-S1) at 5 electrodes surrounding Cz following administration of CVN058 compared to placebo.
- Pre-stimulus gamma amplitude following administration of CVN058 compared to placebo
- P300 amplitude and latency at average of 5 centroparietal electrodes around parietal electrodes (Pz) following administration of CVN058 compared to placebo

- MMN amplitude to additional deviants (frequency, intensity, location, frequency-modulation [FM]) and latency to all deviants following administration of CVN058 compared to placebo
- CVN058, its metabolite if appropriate,  $C_{max}$ ,  $t_{max}$ , and area under the plasma concentration-time curve from 0 to the last quantifiable concentration (AUCt).

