**Figure 6.a Schematic of Study Design**

## 5.2 Justification for Study Design, Dose, and Endpoints

This study will explore CNS target engagement by measuring alterations in auditory evoked potentials, similar to the demonstration of an effect on P50 auditory gating using the 5-HT3 antagonist, ondansetron ([Adler, 2005](#)). The study design was based on that published study, adapted for CVN058 as study drug and MMN as the primary endpoint. It has been reported that most subjects with schizophrenia demonstrate a deficit in neural processing that is manifested as a reduction in MMN and impairment of auditory sensory gating (P50). According to Adler et al., ondansetron improves the P50 deficit after a single dose administration ([Adler, 2005](#)).

The study will be a randomized, 3 period crossover study (CVN058 at two dose levels, and placebo) in order to evaluate the effect of CVN058 on MMN as well as on exploratory measures (i.e., P50 auditory gating, gamma power, and P300) compared to placebo. The study will be double-blind and placebo-controlled in order to avoid subjective bias in the assessment of the PD markers. In addition, conduct of study procedures for each subject will occur at approximately the same time per day across each of the Treatment Periods to avoid diurnal changes that may otherwise confound the analysis.

The 150 mg level of CVN058 is expected to saturate CNS 5-HT3 receptors throughout the EEG session, but is 50% lower than the highest dosage for which safety and tolerability has been demonstrated in previous phase 1 studies in healthy subjects, thus presumably maximizing the PD signal within the established limits of safe use. The lower dose level of 15 mg CVN058 is expected to attain a lower CNS 5-HT3 receptor occupancy, decreasing to possibly 70-80% by the end of the EEG session. The 10-fold difference in these dosages should help establish a dose-response relationship for evoked response potential (ERP) effects of CVN058. From a safety perspective, single doses ranging from 5 mg to 300 mg CVN058 have been safe and well-

tolerated. Daily doses of 25, 75, and 150 mg of CVN058 for 7 days have also been studied, and were similarly safe and well-tolerated.

The timing of dosing was selected to allow the EEG assessments to occur at the corresponding estimated  $t_{max}$  values of CVN058. The length of the washout periods is considered adequate based on the PK profile of CVN058.

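### Resting EEG power from ten 1-second epochs leaves the 0.5–1 Hz part of the stated delta band unresolved and adds avoidable sampling noise to every band (low priority)

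*Protocol*

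**What the plan says.** The resting EEG paragraph of section 8.1.16 (Version 2.0) has three relevant elements.

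- Recording: "Five minute eyes open/close recordings will be obtained during each recording session".
- Data analysed: "Ten 1-second, artifact-free epochs will be chosen for quantitative analysis".
- Outcome: "power within delta (0.5 – 4 Hz), theta (4-7 Hz), alpha (8-13 Hz), delta (13-20 Hz), low gamma (20-40 Hz"). The sixth band runs from 40 to 60 Hz and is labelled high gamma; all six are taken over pre-designated scalp regions.

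Section 9.1.16 of Version 1.0 reads the same. The label delta is used for both 0.5–4 Hz and 13–20 Hz; below, delta means 0.5–4 Hz.

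The text does not say whether five minutes, or ten epochs, applies to the session or to each eye condition. It names no window and no rule for choosing the epochs. The opening of 8.1.16 adds: "All EEG parameters will be obtained in accordance with the EEG acquisition guideline provided by Cerevance or their designee". That guideline is not part of the protocol.

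Gamma power is named in the exploratory objectives (4.1.3). The gamma item in the list of exploratory endpoints (4.2.3) is a different quantity: "Pre-stimulus gamma amplitude following administration of CVN058 compared to placebo".

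**The concern.** The protocol itself fixes epoch length, number of epochs and band edges, so this is a stated estimator and not a detail left to the SAP. Two of its parts do not fit together. A 1-second epoch holds half a cycle of a 0.5 Hz wave, yet the delta outcome is defined from 0.5 Hz upward.

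Separately, averaging ten seconds when minutes have been recorded makes each session's value noisier than it need be, and the result varies with the ten seconds taken. The noise enters both sessions of every drug–placebo difference. The crossover was adopted so that each subject serves as own control and variability falls (3.4); this rule gives some of that back, in a trial of about 20 completed subjects.

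**Working it through.** The protocol states no figure for the precision of band power, so there is none to reproduce.

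**1. Share of the recording used.** Inputs from 8.1.16: ten epochs of 1 s; five minutes = 300 s.

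| Reading | Used / recorded | Share |
|---|---|---|
| Ten epochs, five minutes in all | 10 / 300 s | 3.3% |
| Ten epochs, five minutes per eye condition | 10 / 600 s | 1.7% |
| Ten epochs per condition, five minutes in all | 20 / 300 s | 6.7% |
| Ten epochs and five minutes per condition | 20 / 600 s | 3.3% |

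**2. Frequency resolution.** Bin spacing = 1/T. For T = 1 s it is 1 Hz, so the bins inside 0.5–4 Hz are 1, 2, 3 and 4 Hz. For T = 2 s it is 0.5 Hz, so the bins are 0.5, 1.0, …, 4.0 Hz (eight), and the lowest falls on the stated edge. With 1-second epochs, low gamma and high gamma hold 21 bins each.

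Share of a pure sinusoid's power that appears in the delta bins of a mean-corrected 1-second epoch, averaged over phase:

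| True frequency | No taper (boxcar) | Hann window |
|---|---|---|
| 0.5 Hz | 55% | 22% |
| 0.75 Hz | 89% | 51% |
| 1 Hz | 100% | 83% |
| 2 and 3 Hz | 100% | 100% |
| 4 Hz | 100% | 83% |
| 5 Hz (outside delta) | 0% | 17% |

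The loss is concentrated below 1 Hz. With a Hann window the upper edge blurs as well.

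**3. Sampling noise, closed form.** For a flat spectrum without taper, the coefficient of variation (CV) of band power ≈ 1/√(epochs × bins).

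- Delta, ten epochs: 1/√(10 × 4) = 15.8%.
- Low or high gamma, ten epochs: 1/√(10 × 21) = 6.9%.
- If all 300 s were clean: delta 1/√(300 × 4) = 2.9%; gamma 1/√(300 × 21) = 1.3%.

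Epoch length as such does not drive this; the total number of seconds does. For 60 s of delta, 60 × 4 = 240 and 30 × 8 = 240, so 1-second and 2-second epochs both give 6.5%.

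**4. Sampling noise with a Hann window.** Simulation of stationary white noise, 1,500 replicates, 1-second epochs:

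| Band | 10 epochs | 60 epochs | 150 epochs |
|---|---|---|---|
| Delta 0.5–4 Hz | 20.2% | 8.4% | 5.4% |
| Alpha 8–13 Hz | 17.1% | 7.2% | 4.4% |
| Low gamma 20–40 Hz | 9.5% | 3.9% | 2.4% |
| High gamma 40–60 Hz | 9.3% | 3.9% | 2.5% |

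For a difference of two sessions, multiply by √2: low gamma with ten epochs 9.5 × 1.41 = 13.4%.

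**5. Does it matter against other variation?** The protocol gives no session-to-session variation. As an assumption, let its CV (excluding sampling error) be 20–40%. Total CV = √(session² + sampling²).

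- Low gamma, session CV 20%: √(400 + 90.25) = 22.1% with ten epochs; √(400 + 15.21) = 20.4% with 60. Reduction 8%.
- Low gamma, session CV 40%: √(1600 + 90.25) = 41.1%; √(1600 + 15.21) = 40.2%. Reduction 2%.
- Delta, session CV 20%: √(400 + 408.04) = 28.4%; √(400 + 70.56) = 21.7%. Reduction 24%.
- Delta, session CV 40%: √(1600 + 408.04) = 44.8%; √(1600 + 70.56) = 40.9%. Reduction 9%.

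**The case against.** The case for leaving the plan alone has real substance.

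- *The unresolved range touches no listed endpoint.* Delta is in neither the exploratory objectives nor the exploratory endpoints, and gamma is not limited by 1 Hz spacing. This stands, and it limits the importance of the resolution problem.
- *The link to the gamma endpoint is weak.* The listed endpoint is pre-stimulus gamma amplitude, whereas these epochs come from resting recordings. MMN does not use them. This stands too. What remains is gamma power as named in the objective and as an outcome of this paragraph.
- *A selection rule may exist elsewhere.* A reader might infer that someone picks the epochs by eye. The text says only that they are chosen; the acquisition guideline or the SAP may give a rule, so its absence here is no fault. Nor can treatment-related bias be inferred, given "The study will be double-blind and placebo-controlled in order to avoid subjective bias in the assessment of the PD markers". What stands is narrower: under any rule that keeps ten seconds out of minutes, the value depends on which ten are kept.
- *The rest may not be usable.* A reader might infer that about 97% of good data is thrown away. The documents give no artifact rate, so only the recorded share is known. The 60-second case allows for heavy artifact loss and still more than halves the sampling CV.
- *The noise model is idealised.* Stationary white noise and a Hann window are assumptions; without taper the gamma figure is about 7%, not 9.5%. The advantage of more data appears under both.
- *A fixed count gives equal data per session, and a minimum-data rule could create missing sessions.* Both parts are fair, so the fix sets no exclusion threshold.

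**Conclusion.** The point holds, at low priority. The stated method does not deliver the lowest part (0.5–1 Hz) of the delta band it names. It also gives each session value an avoidable sampling CV of about 20% for delta and 9.5% for gamma, against about 8% and 4% with 60 clean seconds. These figures assume stationary white noise and a Hann window. For gamma, moving to 60 s lowers total variation by only about 2–8% if session CV is 40–20%.

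It would go too far to say that 1-second epochs cannot measure delta: bins at 1, 2, 3 and 4 Hz give a coarse estimate from about 1 to 4 Hz. It would also go too far to read this as a threat to the primary result or to the listed gamma endpoint.

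One limit is the version. The wording is in Versions 1.0 and 2.0; the available text of Version 3.0 stops before this section, and Versions 4.0 and 5.0 are not shown. The criticism applies to the current plan only if the sentence was kept.

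**What to change.** First check whether the sentence persists in Versions 3.0–5.0. If it does, replace it with:

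> All artifact-free 2-second epochs (overlapping windows allowed) from each recording will be used, with the same artifact-rejection rule applied to every session blind to treatment.

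Report the clean seconds per session, and do not exclude sessions below 60 s.

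Two-second epochs put a bin at the stated 0.5 Hz edge, and using every clean epoch removes the choice among them. The cost is one sentence and some reprocessing of data already recorded; no extra recording, visit or subject burden follows. The downside is that the amount of data, and hence the precision, differs between sessions, which is why clean seconds should be reported. With a taper, the 0.5 Hz bin of a 2-second epoch still picks up some slow drift, so the lowest bin needs cautious reading even after the change.

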## **P300**

As opposed to MMN, which are obtained under passive (i.e., no-task) conditions, auditory P300 will be obtained only when subjects must attend to and detect novel task-relevant deviant stimuli. Generators for P300 are located in distributed frontoparietal networks and so represent an index of higher order, “cognitive” processing in schizophrenia. P300 will be obtained to deviant auditory stimuli in an auditory “oddball” paradigm. P300 is maximal in amplitude at Fz and Pz electrodes. Primary outcome measures will consist of peak amplitude within prespecified latency range at the frontal/parietal sites.

### **8.1.17 Positive and Negative Syndrome Scale**

The PANSS was developed and standardized for typological and dimensional assessment of schizophrenic phenomena. In this study, empirically derived factors are tested excluding those items that could not be assessed during the test sessions: positive symptom factor (delusions, unusual thoughts, somatic concern, grandiosity, suspiciousness, and hallucinations), negative symptom factor (emotional withdrawal, blunted affect, poor rapport, disturbance of volition, preoccupation, and motor retardation), cognitive factor (difficulty in abstract thinking, stereotyped thinking, cognitive disorganization, lack of judgment and insight, poor attention, tension, mannerisms, and posturing), hostility (excitement, hostility, impulse control, and uncooperativeness), emotional discomfort (depression, anxiety, and guilt). PANSS will be collected at Screening, Early Termination, and at the Follow-up Visit if clinically significant findings were observed upon discharge. In these cases, subjects must then be brought back to the clinic for re-evaluation per investigator’s discretion.

The duration of the PANSS is approximately 30 minutes ([Kay, 1990](#)).

### **8.1.18 Columbia Suicide Severity Rating Scale**

The determination and management of patients' suicidality risk is the Investigators' responsibility. For study purposes, suicidality will be assessed by the use of the C-SSRS. The C-SSRS is a 3-part scale that measures suicidal ideation (e.g., subject endorses thoughts about a wish to be dead or has other thoughts of suicide), intensity of ideation (frequency, duration, controllability, deterrents, and reasons for ideation), and suicidal behavior (actually, interrupted, and aborted attempts at suicide) ([Mundt, 2013](#)).

The C-SSRS is a 2-page questionnaire that prospectively assesses suicidal thoughts and behavior using a structured interview for patient responses. Suicidal ideation is classified on a 5-item scale: 1 (wish to be dead), 2 (nonspecific active suicidal thoughts), 3 (active suicidal ideation with any methods [not plan] without intent to act), 4 (active suicidal ideation with some intent to act, without specific plan), and 5 (active suicidal ideation with specific plan and intent). The C-SSRS also captures information about the intensity of ideation, specifically the frequency, duration, controllability, deterrents, and reasons for the most severe types of ideation. Suicidal behavior is classified on a 5-item scale: 0 (no suicidal behavior), 1 (preparatory acts or behavior), 2 (aborted attempt), 3 (interrupted attempt), and 4 (actual attempt).

Different versions of the scale are available. In this study, "Baseline/Screening" version will be used at Screening Visit and "Since last visit" version at all subsequent visits. "Since the last visit" should collect information from the last visit where C-SSRS was administered. If the patient's response generates a change in the findings report from negative to positive, the patient should be referred for immediate psychiatric evaluation on the same date as the site visit.

Positive suicidality findings, if confirmed by the PI, is considered to be a serious event. If arising after signing informed consent but prior to administration of any study medication, it is considered a Pretreatment Event (PTE). If arising after administration of any study medication, it is considered an SAE.

The C-SSRS will be administered by the PI or a trained designee on paper and captured in the eCRF. The same interviewer should be used throughout the study for the same subject where possible.

### **8.1.19 Documentation of Screen Failure**

Investigators must account for all subjects who sign informed consent. If the subject is found to be not eligible at this visit, the investigator should complete the eCRF screen failure form.

The primary reason for screen failure is recorded in the eCRF using the following categories:

- PTE/AE.
- Did not meet inclusion criteria or did meet exclusion criteria.
- Significant protocol deviation.
- Lost to follow-up.
- Voluntary withdrawal.

- Study termination.
- Other <specify reason>.

Subject numbers assigned to subjects who fail Screening should not be reused.

### **8.1.20 Documentation of Randomization**

Only subjects who meet all of the inclusion criteria and none of the exclusion criteria are eligible for randomization into the treatment phase. Randomization will take place on Day 1 of Treatment Period 1.

If the subject is found to be not eligible for randomization, the investigator should record the primary reason for failure on the applicable eCRF.

## **8.2 Monitoring Subject Treatment Compliance**

Study medication will be administered while subjects are under observation in the clinical research unit. Following administration of the study medication, appropriate mouth and/or hand checks will be performed to ensure that the dose is swallowed and noted in the source document. The date and time of each dose will be recorded in the source documents and on the eCRFs. An inventory of the study medication supplies dispensed will be performed by the site pharmacist or authorized study designee and recorded onto the Drug Accountability Log in the subject's source document records or equivalent. The exact dose time of consecutive subjects may be staggered to facilitate logistics at the site.

## **8.3 Schedule of Observations and Procedures**

The schedule for all study-related procedures for all evaluations is shown in [Appendix A](#). Assessments should be completed at the designated visit/time point(s).

### **8.3.1 Screening**

Subjects with schizophrenia will be screened within 28 days prior to enrollment. All subjects will be screened in accordance with predefined inclusion and exclusion criteria as described in [Section 7.0](#). See [Section 9.1.17](#) for procedures for documenting screen failures. Following written informed consent, Screening procedures may be conducted on different days. Assessments to be conducted during the Screening period are outlined in [Appendix A](#).

### **8.3.2 Treatment Phase**

The treatment will be administered over 3 Periods, separated by 7-10 days for washout. Assessments to be conducted during the screening period are outlined in [Appendix A](#).

### **8.3.3 Final Visit/End of Treatment**

The Final Visit additional assessments will occur prior to Discharge from the clinic at the end of Treatment Period 3, Day 1, as outlined in [Appendix A](#).

For all subjects who received any study medication, the investigator must complete the End of Study eCRF page.

### **8.3.4 Early Termination**

The reason for discontinuation must be documented in the source document and eCRF. The procedures outlined in [Appendix A](#) will be performed and documented.

For all subjects receiving study medication, the investigator must complete the End of Study eCRF page.

### **8.3.5 Follow-up Visit/Telephone Call**

The Follow-up Visit will occur by telephone approximately 7-10 days after receiving the last dose of study medication (Treatment Period 3) unless abnormal, clinically significant findings were observed upon discharge. In these cases, subjects must then be brought back to the clinic for re-evaluation per investigator's discretion.

## **8.4 Biological Sample Retention and Destruction**

In this study, specimens for genome/gene analysis will be collected as described in [Section 9.1.12](#), Pharmacogenomic Sample Collection. The genetic material will be preserved and retained by a biorepository contracted by Cerevance for up to but not longer than 15 years or as required by applicable law.

The samples will be sent to a central laboratory that processes the blood sample and serves as a secure storage facility. The sponsor and researchers working with the sponsor will have access to the samples collected and any test results. All samples collected during the study will be stored securely with limited access and the sponsor will require anyone who works with the samples to agree to hold the research information and any results in confidence.

The sample will be labeled with a unique sample identifier similar to labeling in the main study. During the “storage” stage, the sample will be used in the analysis of the study drug and related disease states. At this stage, sample and data are linked to personal health information with code numbers. This link means that patients may be identifiable but only indirectly. The code numbers will be kept secure by the sponsor.

Subjects who consented and provided a pharmacogenomic sample for DNA and RNA analysis can withdraw their consent and request disposal of a stored sample at any time prior to analysis. Notify sponsor of consent withdrawal.

